6.2.6. Multiple measurements at One Visit

If there is more than one assessment reported under a nominal visit (for example data reported at the nominal and associated unscheduled visits), the first assessment will be used for summary tables and analyses. All assessments will be listed.

For safety assessments such as ECG the most abnormal result will be reported for the visit based on the following hierarchy: Abnormal-Clinically Significant > Abnormal – not clinically significant > Normal.

Where triplicate ECG measures are taken, the average of the triplicates will be used for summary statistics, and in the evaluation of the highest post-baseline measure.

For laboratory assessments, participants with post-baseline safety data in both High and Low categories with respect to the Normal Range/Potential Clinical Concern will be counted in each of the categories for the “Any visit post-baseline” row of related summary tables.

6.2.7. Handling of Partial Dates

Element	Reporting Detail				
General	Partial dates will be displayed as captured in participant listing displays. However, where necessary, display macros may impute dates as temporary variables for sorting data in listings only. In addition, partial dates may be imputed for ‘slotting’ data to study phases or for specific analysis purposes as outlined below.				
Exacerbations and Adverse Events	
Partial dates for exacerbations and AEs recorded in the CRF will be imputed using the following imputations:
 
 
 Partial Start Date	'01' will be used for a missing day and 'Jan' will be used for a missing month. If this results in a date prior to the start of study treatment then the treatment start date will be used. The event will then be considered to be ‘On-treatment’ as per Section 6.2.2.	
 
 Partial End Date (for Exacerbations)	'28/29/30/31' will be used for a missing day (dependent on the month and year) and 'Dec' will be used for a missing month. If this results in a date after the exit visit date, then the exit visit date will be used.	
 
	Partial Start Date	'01' will be used for a missing day and 'Jan' will be used for a missing month. If this results in a date prior to the start of study treatment then the treatment start date will be used. The event will then be considered to be ‘On-treatment’ as per Section 6.2.2.	Partial End Date (for Exacerbations)	'28/29/30/31' will be used for a missing day (dependent on the month and year) and 'Dec' will be used for a missing month. If this results in a date after the exit visit date, then the exit visit date will be used.
Partial Start Date	'01' will be used for a missing day and 'Jan' will be used for a missing month. If this results in a date prior to the start of study treatment then the treatment start date will be used. The event will then be considered to be ‘On-treatment’ as per Section 6.2.2.				
Partial End Date (for Exacerbations)	'28/29/30/31' will be used for a missing day (dependent on the month and year) and 'Dec' will be used for a missing month. If this results in a date after the exit visit date, then the exit visit date will be used.				

Element	Reporting Detail	
	Partial End Date (for Adverse Events)	'28/29/30/31' will be used for a missing day (dependent on the month and year) and 'Dec' will be used for a missing month. If this results in a date after the study treatment stop date +28 days, then the study treatment stop date + 28 days will be used.
	Completely missing start/end date	No imputation is applied.
Concomitant Medications/ Medical History	Partial dates for any concomitant medications or medical history conditions recorded in the CRF will be imputed using the following convention:	
	Partial Start Date	'01' will be used for the day and 'Jan' will be used for the month.
	Partial End Date	'28/29/30/31' will be used for the day (dependent on the month and year) and 'Dec' will be used for the month.
	Completely missing start/end date	No imputation is applied.

6.3. Appendix 3 Exclusions from Per-Protocol Population

The per-protocol population includes all participants in the mITT who do not have protocol deviations that may significantly impact the interpretation of efficacy results.

Specifically, a participant will be excluded from the per-protocol population if meeting any of the following criteria that could significantly impact the interpretation of efficacy results:

Number	Exclusion Description
01	Informed consent never signed
02	Did not meet at least one of the following inclusion criteria (as numbered in the protocol) 
 1. Participant must be at least 40 years of age at Screening Visit 1 3. COPD Diagnosis: Documented history of COPD of at least 1 year in accordance with the definition by the American Thoracic Society/European Respiratory Society 7. Smoking status: Current or former cigarette smokers
03	Met at least one of the following exclusion criteria (as numbered in the protocol) 
 1. Asthma: Participants with a past history or concurrent diagnosis of asthma 2. Other respiratory disorders: The Investigator must judge that COPD is the primary diagnosis 4. Lung resection: Participants with lung volume reduction surgery within the 12 months prior to Screening Visit 1. 10. Eosinophilic Disease: Participants with other conditions that could lead to elevated Eosinophils 11. Parasitic Infection: Participants with a known, pre-existing parasitic infestation within 6 months prior to Screening Visit 1. 15. Previous mepolizumab studies: Participants who have received interventional product in previous mepolizumab studies 17. Investigational Medications: Participants who have received an investigational drug within 30 days of Visit 1, or within 5 drug half-lives of the investigational drug
04	Did not meet the following randomization inclusion criteria (as numbered in protocol) 
 1. Blood eosinophil count: Participants that do not have a historical blood eosinophil count that satisfies screening inclusion criterion 2 (Protocol Section 5.1) must have Screening Visit 1 blood eosinophil count ≥ 150 cells/μL.
05	Use of prohibited medication during the study ^[1]
06	Occurrence of any one of the following treatment related deviations for ≥ 2 consecutive doses or ≥ 3 doses at any time during the study: 
 Received study treatment to which they were not randomized Study treatment not administered per protocol Expired study treatment administered

Number	Exclusion Description
	Use of study treatment impacted by a temperature excursion which was not reported or approved, or which was disapproved for further use
07	Participant/investigator is unblinded

[1] See Section 6.5.3 of protocol for prohibited medications.

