Mepolizumab is a humanised immunoglobulin G (IgG) antibody (IgG1, kappa) which binds to and inhibits the ability of IL-5 to bind to the IL-5 receptor. IL-5 receptors are primarily expressed on eosinophils. IL-5 is a major regulator of eosinophils and upon binding to the IL-5 receptor results in accumulation in tissues and modulation of eosinophil behaviour from maturation to survival. Mepolizumab can reduce eosinophils in the periphery and in tissues.

Two 52-week, randomized, placebo-controlled, double-blind, parallel-group, multi-center initial Phase IIIA studies, MEA117106 and MEA117113, evaluated the effect of mepolizumab, administered every 4 weeks through subcutaneous (SC) injection, on the rate of moderate/severe COPD exacerbations in participants with a history of COPD exacerbations despite receiving ICS-based triple maintenance therapy [Pavord, 2017]. Studies MEA117106 and MEA117113 demonstrated that treatment with mepolizumab

led to improvements in exacerbations and other efficacy endpoints when compared with placebo. In addition, in these studies, the safety profile of mepolizumab was similar to placebo and no new safety concerns were identified in this COPD patient population to those identified in the severe asthma program.

The results from MEA117113 and MEA117106 demonstrate that while patients selected with an exacerbating phenotype and with a blood eosinophil count ≥ 150 cells/ μL at Screening or ≥ 300 cells/ μL in previous 12 months achieved a clinically relevant reduction in moderate/severe exacerbations, patients with a blood eosinophil count ≥ 300 cells/ μL (in previous 12 months or at Screening) are more likely to achieve greater benefit from mepolizumab. Thus, a blood eosinophil count ≥ 300 cells/ μL provides a clear threshold to identify patients that are more likely to benefit from mepolizumab. In this study, to ensure stability of eosinophil counts, an additional requirement is for a documented historical eosinophil count of ≥ 150 cells/ μL in the 12 months prior to Screening Visit 0. Participants with no documented historical eosinophil count of ≥ 150 cells/ μL must meet this threshold at the Screening Visit 1 assessment prior to randomization.

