9.3. Populations for Analyses

For purposes of analysis, the following populations are defined:

Population	Description
All Participants Enrolled (ASE)	All participants for whom a record exists on the study database. This population will be used for summarizing reasons for screen and run-in failures.
Modified Intent-to-Treat (mITT)	All randomized participants who receive at least one dose of trial medication. Primary population for analysis of efficacy endpoints data by randomized treatment arm.
Safety	All randomized participants who receive at least one dose of trial medication. Analysis of safety endpoints by actual treatment received for more than 50% of treatment administrations.
Per-Protocol (PP)	All participants in the mITT population not identified as protocol deviators with respect to criteria that are considered to impact the primary efficacy endpoint. Population for supplementary analysis of primary endpoint.

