9.4.1. Efficacy Analyses

Endpoint	Statistical Analysis Methods
Primary	
The primary estimand is defined by the following attributes:
 
Population: Participants with COPD experiencing frequent exacerbations and characterized by eosinophil levels
 
Treatment comparison: Mepolizumab vs. placebo (both as add-on treatment to standard of care)
 
Variable: Number of moderate or severe exacerbations
 
Summary Measure : Ratio of the frequency of exacerbations in the mepolizumab treatment arm to the frequency in the placebo arm. Exacerbation rates will be expressed as an annualized exacerbation rate p.a.
 
Strategies for intercurrent events:
 
A treatment policy strategy will be used for the intercurrent events of discontinuation of study medication, use of medication prohibited by the protocol, and investigational product interruption of 2 or more doses, when these intercurrent events are not associated with disruptions or restrictions imposed due to the COVID-19 pandemic.
 
A hypothetical strategy will be considered when these intercurrent events have occurred as a result of disruptions or restrictions (e.g. lockdown measures, social distancing) imposed due to the COVID-19 pandemic. Full details will be provided in the RAP.
 
The target population for the estimand is as defined by the study inclusion/exclusion criteria and therefore the modified Intent-to-Treat population will be the primary population for efficacy analyses.
 
Participants who prematurely discontinue study treatment (for any reason) will not be required to withdraw from the study and every effort will be made by the

Endpoint	Statistical Analysis Methods

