1.1.2. Primary Estimand

The primary estimand is the difference between mepolizumab 100 mg SC and placebo (both added to optimized standard of care) in the annualized rate of moderate/severe exacerbations in participants with COPD experiencing frequent exacerbations and characterized by eosinophil levels, regardless of IP discontinuation/interruption or changes in background medication/starting a prohibited medication, in the absence of COVID-19 pandemic related intercurrent events.

The primary estimand is described by the following attributes:

Population: Participants with COPD experiencing frequent exacerbations and characterized by eosinophil levels

Treatment condition: Mepolizumab 100 mg SC vs. placebo (both as add-on treatment to optimized standard of care)

Variable: Number of moderate or severe exacerbations

Intercurrent events: The anticipated intercurrent events in this trial are discontinuation of interventional product (IP), interruption of 2 or more consecutive doses of IP, use of prohibited medications and change in background medication.

A treatment policy strategy will be used to handle the intercurrent events of discontinuation of IP and interruption of 2 or more consecutive doses of IP when not associated with disruptions or restrictions (e.g. lockdown measures, social distancing) imposed due to the COVID-19 pandemic. Under this strategy exacerbations and time in study will be included in the analysis regardless of the intercurrent event. A hypothetical strategy will be used to handle these intercurrent events when they are known to be associated with disruptions or restrictions imposed due to the COVID-19 pandemic. A treatment policy strategy will be used to handle the intercurrent events of change in background medication and use of prohibited medications.

Rationale for estimand: The use of a hypothetical strategy recognizes any effect on exacerbations due to discontinuation or interruption of 2 or more consecutive doses of IP associated with disruptions or restrictions imposed due to the COVID-19 pandemic, may not have occurred in the hypothetical scenario of the absence of the pandemic.

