6.1.3. Protocol Deviations

Important protocol deviations will be summarized.

Protocol deviations will be tracked by the study team throughout the conduct of the study and reviewed in accordance with the Study Deviations Rules Document dated 24 August 2022 (Version 5) or later. Protocol deviations classified as important are detailed in the Study Deviations Rules Document and those requiring exclusion from the Per-Protocol (PP) population are provided in Section 6.3.

- Data will be reviewed prior to unblinding and locking the database to ensure all important deviations are captured and categorized in the protocol deviations dataset.
- Protocol deviations related to study treatment assignment will be confirmed as protocol deviations following unblinding for participants who received incorrect treatment according to the randomized treatment.
- This dataset will be the basis for the summaries of important protocol deviations.

Protocol deviations which result in exclusion from the per-protocol analysis set will also be summarized.

Data will be reviewed prior to unblinding and locking the database to ensure all deviations leading to analysis population exclusions are captured and categorized in the protocol deviations ADaM dataset (note these exclusions are not captured in the SDTM dataset).

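### The per-protocol exclusion list removes failures of the 150-cell fallback check but keeps participants who fail the 300-cell entry threshold or the exacerbation-history criterion

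*SAP*

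**What the plan says.** Protocol 9.3 defines PP as "All participants in the mITT population not identified as protocol deviators with respect to criteria that are considered to impact the primary efficacy endpoint" and gives it one use, a supplementary analysis of the primary endpoint. SAP 3 repeats this and requires exclusions to be decided before unblinding.

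SAP 6.3 turns the definition into a list. Its test is "protocol deviations that may significantly impact the interpretation of efficacy results". SAP 6.1.3 makes the list operative: "those requiring exclusion from the Per-Protocol (PP) population are provided in Section 6.3". The entries on eligibility are:

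- Item 02, "Did not meet at least one of the following inclusion criteria (as numbered in the protocol": criteria 1, 3 and 7 only.
- Item 03: selected exclusion criteria, including asthma, other eosinophilic disease and parasitic infection.
- Item 04, "Did not meet the following randomization inclusion criteria (as numbered in protocol": randomization inclusion criterion 1, a Visit 1 count of at least 150 cells/µL where no qualifying historical count exists.

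The other items cover consent, prohibited medication, dosing deviations and unblinding.

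Protocol 5.1 criterion 2 also requires at least 300 cells/µL at Visit 0. Criterion 5 requires two or more moderate exacerbations treated with systemic corticosteroids, or at least one severe exacerbation, in the prior 12 months. SAP 1.1.2 describes the estimand population as "participants with COPD experiencing frequent exacerbations and characterized by eosinophil levels".

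**The concern.** The list enforces the secondary eosinophil check and not the main one. Suppose one participant is randomized in error with a Visit 0 count of 200 and a historical count of 160: that participant stays in PP. Another has a Visit 0 count of 400, no qualifying historical count and a Visit 1 count of 140: that participant is removed.

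The protocol gives the 300-cell threshold the greater weight. Protocol 2.1 says it "provides a clear threshold to identify patients that are more likely to benefit from mepolizumab", and Protocol 4.2 gives the same reason for choosing it. Protocol 2.1 explains the 150-cell requirement only as a check that counts are stable. For exacerbation history, Protocol 2.2 cites evidence that previous exacerbations are the best single predictor of later ones, and the primary model in SAP 4.2.2 adjusts for them.

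At stake is how the PP result can be read. Followed exactly, the list leaves in PP people who lack one of the two features by which the estimand population is named.

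**Working it through.** **1. Comparing the lists.** Protocol 5.1 has nine inclusion criteria. SAP 6.3 items 02 and 04 reach criteria 1, 3 and 7 and the Visit 1 fallback part of criterion 2. They do not reach the Visit 0 part of criterion 2, or criteria 4, 5, 6 and 8; item 01 covers the absence of signed consent (criterion 9). No other SAP section adds a PP exclusion.

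**2. Whether other analyses fill the gap.** SAP 4.2.5 models the treatment effect by screening eosinophil count, and SAP 4.10.1 has subgroups by prior exacerbations. Both help in part. The lowest prior-exacerbation band (2 or fewer), used as subgroup and covariate, mixes criterion 5 failures with eligible participants who had two moderate events or one severe event. SAP 6.1.3 tabulates important deviations but does not re-run the model without them.

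**3. Precision under the plan's own inputs.** Protocol 9.2 and 9.2.1 give a placebo rate of 1.7, a 23% reduction (mepolizumab rate 1.7 × 0.77 = 1.309), dispersion 0.55 and 756 participants (378 per arm) with 52 weeks of follow-up.

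n per arm = (1.960 + 1.282)² × (1/1.7 + 1/1.309 + 2 × 0.55) / (ln 0.77)² = 377.2, so 378 per arm and 756 in total. Allowing for 5.5% missing data, 756/0.945 = 800. Both match the plan.

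SE(log rate ratio) = √[(1/1.7 + 1/1.309 + 1.1)/378] = 0.0805. The 95% interval around 0.77 is 0.658 to 0.902, a reduction of 9.8% to 34.2%.

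**4. Dilution.** Let f be the share of PP who are deviators (balanced between arms, equal follow-up), r their placebo rate relative to eligible participants, and RRd their rate ratio. All three are assumptions. Then

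RR in PP = [(1 − f) × 0.77 + f × r × RRd] / [(1 − f) + f × r].

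Reduction read from PP when the true value is 23% (shift in SE units in brackets):

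| f | RRd = 1, r = 1 | RRd = 1, r = 0.5 | RRd = 0.82, r = 1 |
|---|---|---|---|
| 2% | 22.54% (0.07) | 22.77% (0.04) | 22.90% |
| 5% | 21.85% (0.18) | 22.41% (0.09) | 22.75% |
| 10% | 20.70% (0.37) | 21.79% (0.19) | 22.50% |

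Example, f = 10%, r = 0.5: (0.693 + 0.05)/0.95 = 0.7821; ln(0.7821/0.77) = 0.0156; 0.0156/0.0805 = 0.19. The value 0.82 is the smaller effect reported for 100 mg in Protocol 4.3, from a broader population.

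At r = 1, a one-point shift needs f = 0.01/0.23 = 4.3% with no benefit (about 35 of 800), or 0.01/0.05 = 20% with an 18% reduction (160 of 800).

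**The case against.** The strongest reply is that the definition is discretionary. PP turns on criteria considered to affect the endpoint, and the sponsor does the considering. That stands. A reader might infer that SAP 6.3 contradicts the protocol, because Protocol 9.4.1 says "The target population for the estimand is as defined by the study inclusion/exclusion criteria". The documents do not support that reading: the sentence goes on to justify mITT as the primary efficacy population and does not define PP. The point is uneven use of SAP 6.3's own test.

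Second, Visit 0 failures should be rare. Protocol 4.1 stops anyone below 300 before Visit 1. This stands and limits the size. Criterion 5 has no laboratory gate; it rests on documented history, and exacerbations related to laboratory-confirmed COVID-19 must be left out of the count.

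Third, the documents do not show that exacerbation history changes the treatment effect. That is correct. The case for criterion 5 rests on its link to the endpoint and on the estimand population, not on effect modification. For eosinophils the SAP goes further: SAP 4.10.1.1 omits the eosinophil categories from shrinkage because it does not expect exchangeability. Even so, the evidence in Protocol 2.1 counted a value of 300 or more either at screening or in the previous year, so a low Visit 0 count does not by itself mean no benefit.

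Fourth, a missing Visit 0 count might be taken as ineligibility. It should not be. Protocol 8 allows repeat samples for technical reasons, and SAP 4.1.2 has a substitution rule for a missing value.

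Fifth, the Study Deviations Rules Document cited in SAP 6.1.3 is not available here and may explain the choice. It cannot be ruled out as a source of reasons, but SAP 6.1.3 places the PP exclusions themselves in SAP 6.3.

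**Conclusion.** The concern holds as an inconsistency in the PP exclusion list, and it is minor. A reader might infer that the primary result is biased or that PP is invalid; neither follows. PP supports one supplementary analysis, and the mITT test, type I error and sample size do not depend on it.

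The likely effect is well inside the sampling error. With an assumed 2% to 10% of deviators who have no benefit, a 23% reduction would read 22.5% to 20.7% at an equal event rate, or 22.8% to 21.8% at half the event rate. The largest shifts are about 0.37 and 0.19 of a standard error. The lower event rate is the more natural assumption, since Protocol 2.1 and 2.2 link eosinophilic inflammation and previous exacerbations to higher risk. No share of deviators is given in the documents, and the upper end of the range is hard to square with the screening gate.

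**What to change.** Before unblinding, add two entries to SAP 6.3 item 02:

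- (a) a documented Visit 0 count below 300 cells/µL, judged on the Visit 0 sample or its valid repeat and not on a missing value alone;
- (b) failure of inclusion criterion 5.

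Identify both through the blinded deviation review already planned in SAP 6.1.3, and report the number excluded for each, by arm. If unblinding has already occurred, run the revised PP analysis and label it post hoc.

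The cost is a short addition to the list and a slightly smaller PP set.

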6.4. Appendix 4: Adverse Events of Special Interest

6.4.1. Systemic Allergic (Type I Hypersensitivity) and Other Systemic Reactions

Systemic reactions will be collected via a targeted eCRF and are required to be assessed against Sampson's diagnostic criteria for anaphylaxis [[Sampson, 2006](#)].

Events reported on the eCRF as systemic reactions will be further categorized by the investigator as an 'allergic (type I hypersensitivity) reaction' or 'systemic other' reaction. Investigators are instructed to report systemic reactions with the best diagnosis/event term that describes the event.

